	Overall	XX (XX.X)	XX (XX.X)	XX (XX.X)
System Organ Class 1				
	Related	XX (XX.X)	XX (XX.X)	XX (XX.X)
	Not Related	XX (XX.X)	XX (XX.X)	XX (XX.X)
	Overall	XX (XX.X)	XX (XX.X)	XX (XX.X)
Preferred Term 1				
	Related	XX (XX.X)	XX (XX.X)	XX (XX.X)
	Not Related	XX (XX.X)	XX (XX.X)	XX (XX.X)
	Overall	XX (XX.X)	XX (XX.X)	XX (XX.X)
Preferred Term 2				
	Related	XX (XX.X)	XX (XX.X)	XX (XX.X)
	Not Related	XX (XX.X)	XX (XX.X)	XX (XX.X)
	Overall	XX (XX.X)	XX (XX.X)	XX (XX.X)

Note 1: A Treatment Emergent Adverse Event (TEAE) is defined as an adverse event that occurs or worsens on or after the first dose of study drug.

Note 2: Subjects with one or more adverse events within a level of MedDRA term is counted only once in that level using the most related incident.

Note 3: System Organ Class (SOC) terms are sorted using alphabetical order. Within each SOC, preferred terms are sorted using alphabetical order.

Note 4: MedDRA Dictionary (Version 23.0) was used for coding adverse events.

Output ID: <Unique Output id i.e. t-enrol> Draft-DDMMYYYY HH:MM:SS DATE OF DATABASE EXTRACTION: DDMMYYYY
<Path/Program Name> Page 1 of X

Table 14.3.1.5
Summary of Treatment-Emergent Serious Adverse Events up to Week 8 by System Organ Class and Preferred Term Safety Analysis set

System Organ Class Preferred Term	Placebo (N=XX)	BBT-401-1S (N=XX)	Overall (N=XX)
Subjects with Any Serious TEAEs up to Week 8	XX (XX.X)	XX (XX.X)	XX (XX.X)
System Organ Class 1	XX (XX.X)	XX (XX.X)	XX (XX.X)
Preferred Term 1	XX (XX.X)	XX (XX.X)	XX (XX.X)
Preferred Term 2	XX (XX.X)	XX (XX.X)	XX (XX.X)
...			
System Organ Class 2	XX (XX.X)	XX (XX.X)	XX (XX.X)
Preferred Term 1	XX (XX.X)	XX (XX.X)	XX (XX.X)
Preferred Term 2	XX (XX.X)	XX (XX.X)	XX (XX.X)
...			
System Organ Class 3	XX (XX.X)	XX (XX.X)	XX (XX.X)
Preferred Term 1	XX (XX.X)	XX (XX.X)	XX (XX.X)
Preferred Term 2	XX (XX.X)	XX (XX.X)	XX (XX.X)

Note 1: A Treatment Emergent Adverse Event (TEAE) is defined as an adverse event that occurs or worsens on or after the first dose of study drug.

Note 2: Subjects with one or more adverse events within a level of MedDRA term is counted only once in that level.

Note 3: System Organ Class (SOC) terms are sorted using alphabetical order. Within each SOC, preferred terms are sorted using alphabetical order.

Note 4: MedDRA Dictionary (Version 23.0) was used for coding adverse events.

Output ID: <Unique Output id i.e. t-enrol>
<Path/Program Name>

Draft-DDMMYYYY HH:MM:SS

DATE OF DATABASE EXTRACTION: DDMMYYYY

Page 1 of X

Table 14.3.1.6
Summary of Treatment-Emergent Adverse Events up to Week 8 Leading to Study Discontinuation by System Organ Class and Preferred Term
Safety Analysis set

System Organ Class Preferred Term	Placebo (N=XX)	BBT-401-1S (N=XX)	Overall (N=XX)
Subjects with Any TEAEs up to Week 8 Leading to Study Discontinuation	XX (XX.X)	XX (XX.X)	XX (XX.X)
System Organ Class 1	XX (XX.X)	XX (XX.X)	XX (XX.X)
Preferred Term 1	XX (XX.X)	XX (XX.X)	XX (XX.X)
Preferred Term 2	XX (XX.X)	XX (XX.X)	XX (XX.X)
...			
System Organ Class 2	XX (XX.X)	XX (XX.X)	XX (XX.X)
Preferred Term 1	XX (XX.X)	XX (XX.X)	XX (XX.X)
Preferred Term 2	XX (XX.X)	XX (XX.X)	XX (XX.X)
...			
System Organ Class 3	XX (XX.X)	XX (XX.X)	XX (XX.X)
Preferred Term 1	XX (XX.X)	XX (XX.X)	XX (XX.X)
Preferred Term 2	XX (XX.X)	XX (XX.X)	XX (XX.X)

Note 1: A Treatment Emergent Adverse Event (TEAE) is defined as an adverse event that occurs or worsens on or after the first dose of study drug.

Note 2: Subjects with one or more adverse events within a level of MedDRA term is counted only once in that level.

Note 3: System Organ Class (SOC) terms are sorted using alphabetical order. Within each SOC, preferred terms are sorted using alphabetical order.

Note 4: MedDRA Dictionary (Version 23.0) was used for coding adverse events.

Output ID: <Unique Output id i.e. t-enrol>
<Path/Program Name>

Draft-DDMMYY HH:MM:SS

DATE OF DATABASE EXTRACTION: DDMMYY

Page 1 of X

Table 14.3.2.1
Summary of Values and Changes of Hematology Parameters by Visit
Safety Analysis Set

Laboratory Group: XXXXXXXXX

Laboratory Test: XXXXXXXXX (Unit)

Study Visit	Placebo (N=XX)	BBT-401-1S (N=XX)	Overall (N=XX)
Baseline			
n (missing)	XX (XX)	XX (XX)	XX (XX)
Mean (SD)	XX.X(X.XX)	XX.X(X.XX)	XX.X(X.XX)
Median	XX.X	XX.X	XX.X
Min, Max	XX, XX	XX, XX	XX, XX
Visit XX			
n (missing)	XX (XX)	XX (XX)	XX (XX)
Mean (SD)	XX.X(X.XX)	XX.X(X.XX)	XX.X(X.XX)
Median	XX.X	XX.X	XX.X
Min, Max	XX, XX	XX, XX	XX, XX
Visit XX - Change from Baseline			
n (missing)	XX (XX)	XX (XX)	XX (XX)
Mean (SD)	XX.X(X.XX)	XX.X(X.XX)	XX.X(X.XX)
Median	XX.X	XX.X	XX.X
Min, Max	XX, XX	XX, XX	XX, XX
...			

Output ID: <Unique Output id i.e. t-enrol>
<Path/Program Name>

Draft-DDMMYYYY HH:MM:SS

DATE OF DATABASE EXTRACTION: DDMMYYYY

Page 1 of X

Table 14.3.2.2
Summary of Values and Changes of Chemistry Parameters by Visit
Safety Analysis Set

Laboratory Group: XXXXXXXXX

Laboratory Test: XXXXXXXXX (Unit)

Study Visit	Placebo (N=XX)	BBT-401-1S (N=XX)	Overall (N=XX)
Baseline			
n (missing)	XX (XX)	XX (XX)	XX (XX)
Mean (SD)	XX.X(X.XX)	XX.X(X.XX)	XX.X(X.XX)
Median	XX.X	XX.X	XX.X
Min, Max	XX, XX	XX, XX	XX, XX
Visit XX			
n (missing)	XX (XX)	XX (XX)	XX (XX)
Mean (SD)	XX.X(X.XX)	XX.X(X.XX)	XX.X(X.XX)
Median	XX.X	XX.X	XX.X
Min, Max	XX, XX	XX, XX	XX, XX
Visit XX - Change from Baseline			
n (missing)	XX (XX)	XX (XX)	XX (XX)
Mean (SD)	XX.X(X.XX)	XX.X(X.XX)	XX.X(X.XX)
Median	XX.X	XX.X	XX.X
Min, Max	XX, XX	XX, XX	XX, XX
...			

Output ID: <Unique Output id i.e. t-enrol>
<Path/Program Name>

Draft-DDMMYYYY HH:MM:SS

DATE OF DATABASE EXTRACTION: DDMMYYYY

Page 1 of X

Table 14.3.3.1
Summary of Vital Sign Parameters by Visit
Safety Analysis Set

Vital Signs Parameter: XXXXXXXXX (Unit)

Study Visit	Placebo (N=XX)	BBT-401-1S (N=XX)	Overall (N=XX)
Baseline			
n (missing)	XX (XX)	XX (XX)	XX (XX)
Mean (SD)	XX.X (X.XX)	XX.X (X.XX)	XX.X (X.XX)
Median	XX.X	XX.X	XX.X
Min, Max	XX, XX	XX, XX	XX, XX
Visit XX			
n (missing)	XX (XX)	XX (XX)	XX (XX)
Mean (SD)	XX.X (X.XX)	XX.X (X.XX)	XX.X (X.XX)
Median	XX.X	XX.X	XX.X
Visit XX - Change from Baseline			
n (missing)	XX (XX)	XX (XX)	XX (XX)
Mean (SD)	XX.X (X.XX)	XX.X (X.XX)	XX.X (X.XX)
Median	XX.X	XX.X	XX.X
Min, Max	XX, XX	XX, XX	XX, XX
...			
...			

Output ID: <Unique Output id i.e. t-enrol>
<Path/Program Name>

Draft-DDMMYYYY HH:MM:SS

DATE OF DATABASE EXTRACTION: DDMMYYYY
Page 1 of X

Table 14.3.3.2
 Summary of Electrocardiogram Parameters by Visit
 Safety Analysis Set

Electrocardiogram Parameter: XXXXXXXXX (Unit)	Placebo (N=XX)	BBT-401-1S (N=XX)	Overall (N=XX)
Study Visit			
Baseline			
n (missing)	XX (XX)	XX (XX)	XX (XX)
Mean (SD)	XX.X (X.XX)	XX.X (X.XX)	XX.X (X.XX)
Median	XX.X	XX.X	XX.X
Min, Max	XX, XX	XX, XX	XX, XX
Visit XX			
n (missing)	XX (XX)	XX (XX)	XX (XX)
Mean (SD)	XX.X (X.XX)	XX.X (X.XX)	XX.X (X.XX)
Median	XX.X	XX.X	XX.X
Min, Max	XX, XX	XX, XX	XX, XX
Visit XX - Change from Baseline			
n (missing)	XX (XX)	XX (XX)	XX (XX)
Mean (SD)	XX.X (X.XX)	XX.X (X.XX)	XX.X (X.XX)
Median	XX.X	XX.X	XX.X
Min, Max	XX, XX	XX, XX	XX, XX
...			

Output ID: <Unique Output id i.e. t-enrol>
 <Path/Program Name>

Draft-DDMMYYYY HH:MM:SS

DATE OF DATABASE EXTRACTION: DDMMYYYY
 Page 1 of X

Table 14.3.3.3
Summary of Physical Examination by Visit
Safety Analysis Set

Body Category: xxxxxxxxxxxx

Study Visit Body Category Status [1]	Placebo (N=XX)	BBT-401-1S (N=XX)	Overall (N=XX)
Baseline	XX (XX.X)	XX (XX.X)	XX (XX.X)
NCS	XX (XX.X)	XX (XX.X)	XX (XX.X)
CS			
Visit XX	XX (XX.X)	XX (XX.X)	XX (XX.X)
NCS	XX (XX.X)	XX (XX.X)	XX (XX.X)
CS			
...			

Output ID: <Unique Output id i.e. t-enrol>
<Path/Program Name>

Draft-DDMMYYYY HH:MM:SS

DATE OF DATABASE EXTRACTION: DDMMYYYY
Page 1 of X

Table 14.4.1.1
 Plasma BBT-401-1S Concentrations (ng/mL) Following the Administration of BBT-401-1S or Placebo
 PK Analysis Set

Study Visit	Placebo (N=XX)	BBT-401-1S (N=XX)
Baseline Pre-dose		
n (missing)	XX (XX)	XX (XX)
Mean (SD)	XX.X (X.XX)	XX.X (X.XX)
Coefficient of Variance (CV %)	XX.X	XX.X
Median	XX.X	XX.X
Min, Max	XX, XX	XX, XX
Baseline 3H Post dose		
n (missing)	XX (XX)	XX (XX)
Mean (SD)	XX.X (X.XX)	XX.X (X.XX)
Coefficient of Variance (CV %)	XX.X	XX.X
Median	XX.X	XX.X
Min, Max	XX, XX	XX, XX
Baseline 6H Post dose		
n (missing)	XX (XX)	XX (XX)
Mean (SD)	XX.X (X.XX)	XX.X (X.XX)
Coefficient of Variance (CV %)	XX.X	XX.X
Median	XX.X	XX.X
Min, Max	XX, XX	XX, XX

...

Output ID: <Unique Output id i.e. t-enrol>
 <Path/Program Name>

Draft-DDMMYYYY HH:MM:SS

DATE OF DATABASE EXTRACTION: DDMMYYYY

Page 1 of X

Table 14.4.2.1
Tissue BBT-401-1S Concentrations (ng/g) Following the Administration of BBT-401-1S or Placebo
PK Analysis Set

Study Visit	Placebo (N=XX)	BBT-401-1S (N=XX)
Colon Screening		
n (missing)	XX (XX)	XX (XX)
Mean (SD)	XX.X(X.XX)	XX.X(X.XX)
Coefficient of Variance (CV %)	XX.X	XX.X
Median	XX.X	XX.X
Min, Max	XX, XX	XX, XX
Rectum Screening		
n (missing)	XX (XX)	XX (XX)
Mean (SD)	XX.X(X.XX)	XX.X(X.XX)
Coefficient of Variance (CV %)	XX.X	XX.X
Median	XX.X	XX.X
Min, Max	XX, XX	XX, XX
Colon Week 8		
n (missing)	XX (XX)	XX (XX)
Mean (SD)	XX.X(X.XX)	XX.X(X.XX)
Coefficient of Variance (CV %)	XX.X	XX.X
Median	XX.X	XX.X
Min, Max	XX, XX	XX, XX

Output ID: <Unique Output id i.e. t-enrol>
<Path/Program Name>

Draft-DDMMYYYY HH:MM:SS

DATE OF DATABASE EXTRACTION: DDMMYYYY

Page 1 of X

Listing 16.2.1.1
Patient Disposition

Subject ID	Randomized (Yes/No)	Cohort	Treatment	Dosed (Yes/No)	Analysis Population	Did the subject complete initial 8-week treatment? (Yes/No)	If No, what was the reason for early termination of initial 8-week treatment?	Did the subject complete Visit 6 (Week 16)? (Yes/No)
xx-yyy	Yes/No	xxx	xxx	Yes/No	mITT/PP/SAF/PK	Yes/No	xxxx	Yes/No

Output ID: <Unique Output id i.e. t-enrol>
<Path/Program Name>

Draft-DDMMYYYY HH:MM:SS

DATE OF DATABASE EXTRACTION: DDMMYYYY

Page 1 of X

Listing 16.2.2.1
Inclusion/Exclusion Criteria Findings - Deviations

Subject ID	Criteria Type	Criteria Details	Value
xx-yyy	Inclusion/Exclusion	xxxxxxxxxxxxxxxxxxxxxxxxxxxx	Yes/No
Output ID: <Unique Output id i.e. t-enrol> <Path/Program Name>	Draft-DDMMYYYY HH:MM:SS	DATE OF DATABASE EXTRACTION:	DDMMYYYY Page 1 of X

Programming note:

1. Only include subjects who answer No to any inclusion Criteria or answer Yes to any Exclusion Criteria.
2. For each subject, only display inclusion Criteria with answer = No and Exclusion Criteria with answer = Yes.

Listing 16.2.4.1
Demographics and Baseline Characteristics

Subject ID	Cohort	Treatment	Age (Years)	Gender	Ethnicity	Race
XX-YYY	XXX	XXX	XX	M/F	XXXX	XXXX

Output ID: <Unique Output id i.e. t-enrol> Draft-DDMMYYYY HH:MM:SS DATE OF DATABASE EXTRACTION: DDMMYYYY
<Path/Program Name> Page 1 of X

Listing 16.2.4.2
 Medical History

Subject ID	Cohort/ Treatment	Body System/ Category	Description of Medical History	Date of Onset	Date of Resolution
xx-yyy	xxx/xxxx	xxxxxx	xxxxxxxxxxxx	DD-MMM-YYYY	DD-MMM-YYYY/Ongoing

Subject ID	Cohort/ Treatment	Does the subject have assessed Mayo Score previously? (Yes/No)	Mayo Score Type/Score/Dat e of Assessed	Does the subject have experienced any hospitalizat ions due to UC? (Yes/No)	Date of Hospitaliza tion/ Treatments Received	Does the subject currently have any extraintestinal manifestations of UC? (Yes/No)	Sites	Extraintesti nal Manifestatio ns
xx-yyy	xxx/xxxx	Yes/No	xxxxx/xxx/DD- MMM-YY	Yes/No	DD-MMM- YY/xxxxxx	Yes/No	xxx/xx x/xxx	xxxxx

Subject ID	Cohort/ Treatment	History of Alcoholism and Drug Abuse? (yes/No)	If 'Yes, describe year	Smoking Status	If 'Current smoker', how many cigarettes smoked in a day	Weekly Alcohol Consumption	Has the subject taken any medications and/or UC therapies within 3 months prior to V1 (Screening)? (Yes/No)
xx-yyy	xxx/xxxx	Yes/No	xxxxxxxx	xx		Type/amount/unit	Yes/No

Output ID: <Unique Output id i.e. t-enrol>
 <Path/Program Name>

Draft-DDMMYYYY HH:MM:SS

DATE OF DATABASE EXTRACTION: DDMMYYYY
 Page 1 of X

Listing 16.2.4.3
Prior and Concomitant Medications

Subject ID	Cohort/ Treatment	Medication Name	Start Date	Stop Date	Dose	Dose Form	Unit	Route	Frequency	Indication
xx-yyy	xxx/xxx	xx	DD-MMM- YYYY	DD-MMM- YYYY/Ongoing	xxxx	xxxx	xxxx	xxxx	xxxx	xxxx

Output ID: <Unique Output id i.e. t-enrol> Draft-DDMMYYYY HH:MM:SS DATE OF DATABASE EXTRACTION: DDMMYYYY
<Path/Program Name> Page 1 of X

Listing 16.2.5.1
Study Drug Administration and Log

Subject ID	Cohort /Treatment	Visit	Date of IP Returned	Number of bottles returned	Number of days that IP dosing should be taken during previous treatment period (from last visit date to last dosing date)	Number of days that IP dosing was missed during previous treatment period	Patient Compliance (%)
xx-yyy	xxx/xxx	xxxx	DD-MMM-YYYY/Not Done	xxx	xxxx	xxxx	xxxx

Output ID: <Unique Output id i.e. t-enrol>
<Path/Program Name>

Draft-DDMMYYYY HH:MM:SS

DATE OF DATABASE EXTRACTION: DDMMYYYY

Page 1 of X

Listing 16.2.6.1
Total Mayo Score

Subject ID	Cohort /Treatment	Visit	Date of Local Read Score Assessed	Local Read Score	Central Read Score	Evidence of UC extending proximal to the rectum?	Total Mayo Score
xx-yyy	xxx/xxx	xxxx	DD-MMM-YYYY/Not Done	xxxxx	xxxxx	xxxxx	xxxxx

Output ID: <Unique Output id i.e. t-enrol>
<Path/Program Name>

Draft-DDMMYYYY HH:MM:SS

DATE OF DATABASE EXTRACTION: DDMMYYYY
Page 1 of X

Listing 16.2.6.2
Partial Mayo Score

Subject ID	Cohort /Treatment	Visit	Date of Assessment	Stool Frequency	Rectal Bleeding	Physician's Global Assessment	Partial Mayo Score
xx-yyy	xxx/xxx	xxxx	DD-MMM-YYYY/Not Done	xxxxxx	xxxxxx	xxxxxx	xxxx

Output ID: <Unique Output id i.e. t-enrol>
<Path/Program Name>

Draft-DDMMYYYY HH:MM:SS

DATE OF DATABASE EXTRACTION: DDMMYYYY
Page 1 of X

Listing 16.2.6.3
Histologic Assessment of Endoscopic Biopsy

Subject ID	Cohort /Treatment	Visit	Date	Specimen Region of Origin	Laboratory Test	Results
xx-yyy	xxx/xxx	xxxx	DD-MMM-YYYY		xxxx	xxxxxx

Output ID: <Unique Output id i.e. t-enrol> Draft-DDMMYYYY HH:MM:SS DATE OF DATABASE EXTRACTION: DDMMYYYY
<Path/Program Name> Page 1 of X

Programming note:
For results, present both numerical and character values if available.

Listing 16.2.6.4
Ulcerative Colitis Endoscopic Index of Severity

Subject ID	Cohort /Treatment	Visit	Date of Assessment	Vascular Pattern	Bleeding	Erosions and Ulcers	Score
xx-yyy	xxx/xxx	xxxx	DD-MMM-YYYY/Not Done	xxxxxx	xxxxxx	xxxxxx	xxxx

Output ID: <Unique Output id i.e. t-enrol> Draft-DDMMYY HH:MM:SS DATE OF DATABASE EXTRACTION: DDMMYY
<Path/Program Name>

Page 1 of X

Listing 16.2.6.5
Short Inflammatory Bowel Disease Questionnaire

Subject ID	Cohort /Treatment	Visit	Date and Time of Assessment	Q1: How often has the feeling of fatigue or being tired and worn out been a problem for you during the past 2 weeks?	Q2: How often during the last 2 weeks have you delayed or canceled a social engagement because of your bowel problem?	Q3: How much difficulty have you had, as a result of your bowel problems, doing leisure or sports activities you would have liked to have done during the past 2 weeks?	Q4: How often during the last 2 weeks have you been troubled by pain in the abdomen?	Q5: How often during the last 2 weeks have you felt depressed or discouraged?
xx-yyy	xxx/xxx	xxxx	xxxxxx	xxxxxxxx	xxxxxxxx	xxxxxxxx	xxxxxxxx	xxxxxxxx

Subject ID	Cohort /Treatment	Visit	Date and Time of Assessment	Q6: Overall, in the last 2 weeks, how much of a problem have you had with passing large amounts of gas?	Q7: Overall, in the last 2 weeks, how much of a problem have you had maintaining or getting to, the weight you would like to be at?	Q8: How often during the last 2 weeks have you felt relaxed and free of tension?	Q9: How much of the time during the last 2 weeks have you been troubled by a feeling of having to go to the bathroom even though your bowels were empty?	Q10: How much of the time during the last 2 weeks have you felt angry as a result of your bowel problem?
xx-yyy	xxx/xxx	xxxx	xxxxxx	xxxxxxxx	xxxxxxxx	xxxxxxxx	xxxxxxxx	xxxxxxxx

Output ID: <Unique Output id i.e. t-enrol>
<Path/Program Name>

Draft-DDMMYYYY HH:MM:SS

DATE OF DATABASE EXTRACTION: DDMMYYYY
Page 1 of X

Programming note:
For each question, present both numerical and character responses if available.

Listing 16.2.6.6
Biomarker

Subject ID	Cohort /Treatment	Visit	Biomarker Parameter	Date of Sample	Results
xx-yyy	xxx/xxx	xxxx	xxxx	DD-MMM-YYYY/Not Done	xxxxx

Output ID: <Unique Output id i.e. t-enrol> Draft-DDMMYY HH:MM:SS DATE OF DATABASE EXTRACTION: DDMMYY
<Path/Program Name>

Page 1 of X

Programming note: this should include C-reactive protein [CRP], fecal calprotectin, and fecal lactoferrin.

Listing 16.2.7.1
Adverse Events

Subject ID	Cohort /Treatment	AE Term	Description	Severity	Date of Onset/ Resolution	Outcome	Action taken with Study Drug	Relatedness	Is the adverse event serious? (Yes/No)	Seriousness Criteria	Date of Death
xx-yyy	xxx/xxx	xxxx	xxxxxxxxx	xxxx	DD-MMM-YYYY/ DD-MMM-YYYY/ Ongoing	xxxxxxxx	xxxxxxxx	xxxxxx	Yes/No	xxxxxx	DD-MMM- YYYY

Output ID: <Unique Output id i.e. t-enrol>
<Path/Program Name>

Draft-DDMMYY HH:MM:SS

DATE OF DATABASE EXTRACTION: DDMMYY

Page 1 of X

Listing 16.2.7.2
Serious Adverse Events

Subject ID	Cohort /Treatment	AE Term	Description	Severity	Date of Onset/ Resolution	Outcome	Action taken with Study Drug	Relatedness	Is the adverse event serious? (Yes/No)	Seriousness Criteria	Date of Death
xx-yyy	xxx/xxx	xxxx	xxxxxxxx	xxxx	DD-MMM-YYYY/ DD-MMM-YYYY/ Ongoing	xxxxxxxx	xxxxxx		Yes/No	xxxxxx	DD-MMM- YYYY

Output ID: <Unique Output id i.e. t-enrol>
<Path/Program Name>

Draft-DDMMYY HH:MM:SS

DATE OF DATABASE EXTRACTION: DDMMYY
Page 1 of X

Listing 16.2.7.3

Adverse Events Leading to Permanent Withdrawal of Study Treatment or Discontinuation from the Study

Subject ID	Cohort /Treatment	AE Term	Description	Severity	Date of Onset/ Resolution	Outcome	Action taken with Study Drug	Relatedness	Is the adverse event serious? (Yes/No)	Seriousness Criteria	Date of Death
xx-yyy	xxx/xxx	xxxx	xxxxxxxx	xxxx	DD-MMM-YYYY/ DD-MMM-YYYY/ Ongoing	xxxxxxxx	xxxxxx		Yes/No	xxxxxx	DD-MMM- YYYY

Output ID: <Unique Output id i.e. t-enrol>
<Path/Program Name>

Draft-DDMMYY HH:MM:SS

DATE OF DATABASE EXTRACTION: DDMMYY

Page 1 of X

Listing 16.2.7.4
Adverse Events Leading to Death

Subject ID	Cohort /Treatment	AE Term	Description	Severity	Date of Onset/ Resolution	Outcome	Action taken with Study Drug	Relatedness	Is the adverse event serious? (Yes/No)	Seriousness Criteria	Date of Death	Primary Cause of Death
xx-yyy	xxx/xxx	xxxx	xxxxxxxxx	xxxx	DD-MMM-YYYY/ DD-MMM-YYYY/ Ongoing	xxxxxxxx	xxxxxxxx	xxxxxx	Yes/No	xxxxxxxx	DD-MMM- YYYY	xxxxx

Output ID: <Unique Output id i.e. t-enrol>
<Path/Program Name>

Draft-DDMMYYYY HH:MM:SS

DATE OF DATABASE EXTRACTION: DDMMYYYY
Page 1 of X

Listing 16.2.8.1
Hematology

Subject ID	Cohort /Treatment	Visit	Date of Sample	Laboratory Parameter (Unit)	Results	Evaluation (NCS/CS)
xx-yyy	xxx/xxx	xxxx	DD-MMM-YYYY/Not Done	xxxx	xxxx	NCS/CS

Output ID: <Unique Output id i.e. t-enrol>
DDMMYYYY
<Path/Program Name>

Draft-DDMMYYYY HH:MM:SS

DATE OF DATABASE EXTRACTION:

Page 1 of X

Listing 16.2.8.2
Chemistry

Subject ID	Cohort /Treatment	Visit	Date of Sample	Laboratory Parameter (Unit)	Results	Evaluation (NCS/CS)
xx-yyy	xxx/xxx	xxxx	DD-MMM-YYYY/Not Done	xxxx	xxxx	NCS/CS

Output ID: <Unique Output id i.e. t-enrol> Draft-DDMMYYYY HH:MM:SS DATE OF DATABASE EXTRACTION: DDMMYYYY
<Path/Program Name> Page 1 of X

Listing 16.2.8.4
Vital Signs

Subject ID	Cohort /Treatment	Visit	Date of Assessment	Parameter (Unit)	Results
xx-yyy	xxx/xxx	xxxx	DD-MMM-YYYY/Not Done	xxxx	xxxx

Output ID: <Unique Output id i.e. t-enrol> Draft-DDMMYY HH:MM:SS DATE OF DATABASE EXTRACTION: DDMMYY
<Path/Program Name> Page 1 of X

Listing 16.2.8.5
Electrocardiogram

Subject ID	Cohort /Treatment	Visit	Date and Time of ECG	Parameter (Unit)	Results	Overall Interpretation	If 'NCS' or 'CS', then describe
xx-yyy	xxx/xxx	xxxx	DD-MMM- YYYY/HH:MM/Not Done/Waived per protocol	xxxx	xxxx	xxxxxx	xxxxxx

Output ID: <Unique Output id i.e. t-enrol>
<Path/Program Name>

Draft-DDMMYY HH:MM:SS

DATE OF DATABASE EXTRACTION: DDMMYY

Page 1 of X

Listing 16.2.8.6
Physical Examination

Subject ID	Cohort /Treatment	Visit	Date of Physical Examination	Body Category	Status (NCS/CS)	Abnormal Finding
xx-yyy	xxx/xxx	xxxx	DD-MMM- YYYY/Not Done/Waived per protocol	xxxxxxxx	NCS/CS	xxxxxxxxxxxxxxxx

Output ID: <Unique Output id i.e. t-enrol>
DDMMYYYY
<Path/Program Name>

Draft-DDMMYYYY HH:MM:SS

DATE OF DATABASE EXTRACTION:

Page 1 of X

Listing 16.2.9.1
Individual Plasma Concentration Data

Subject ID	Cohort /Treatment	Visit	Date of Sampling	Time Point	Time of Sampling	Results
xx-yyy	xxx/xxx	xxxx	DD-MMM-YYYY/Not Done	Pre-dose/3H Post dose/6H Post dose	HH:MM/Not Done	xxxx

Output ID: <Unique Output id i.e. t-enrol> Draft-DDMMYYYY HH:MM:SS DATE OF DATABASE EXTRACTION: DDMMYYYY
<Path/Program Name> Page 1 of X

Listing 16.2.9.2
Individual Tissue Concentration Data

Subject ID	Cohort /Treatment	Visit	Date of Sampling	Results
xx-yyy	xxx/xxx	Colon Screening/Rectum Screening/Colon Week 8 /Rectum Week 8	DD-MMM-YYYY/Not Done	xxxx

Listing 16.2.10.1 Randomization

Subject ID	Which cohort is the subject in?	Is this subject eligible to participate in this study? (Yes/No)	If Yes, Randomization Code
xx-yyy	xxx	Yes/No	xxxx

Output ID: <Unique Output id i.e. t-enrol> Draft-DDMMYYYY HH:MM:SS DATE OF DATABASE EXTRACTION: DDMMYYYY
<Path/Program Name> Page 1 of X

Listing 16.2.10.2
IP

Subject ID	Cohort /Treatment	Visit	Dose (mg/day)	IP Code	Date and Time of IP Administration at Site	Date of IP Distributed	Re-distributed IP Codes
xx-yyy	xxx/xxx	xxxx	xxx	xxx	DD-MMM-YYYY/HH:MM/Not Done	DD-MMM-YYYY/Not Done	xxxx/None

Output ID: <Unique Output id i.e. t-enrol>
<Path/Program Name>

Draft-DDMMYYYY HH:MM:SS

DATE OF DATABASE EXTRACTION: DDMMYYYY
Page 1 of X

Listing 16.2.10.3
Investigator Signature

Subject ID	Cohort /Treatment	Did you (Principal Investigator) review all the study information? (Yes/No)	Name	Date	Type
xx-yyy	xxx/xxx	Yes/No	xxxx	xxxx	xxxx

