## 8.3 Efficacy Assessments

- Total Mayo Score (Stool frequency, rectal bleeding, endoscopic findings [flexible proctosigmoidoscopy/colonoscopy], physician's global assessment): Screening and W8
- Partial Mayo Score: Baseline, W4, W8, W12, and W16
- Histologic Assessment of Endoscopic Biopsy: Screening and W8
- UCEIS score: Screening and W8
- SIBDQ: Baseline, W4, W8, W12, and W16
- Serum CRP: Baseline, W4, W8, W12, and W16
- Fecal calprotectin: Baseline, W4, W8, W12, and W16
- Fecal lactoferrin: Baseline, W4, W8, W12, and W16

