### 9.5.1 Analysis of Primary Endpoint

The primary objective is to determine the efficacy of BBT-401-1S in patients with active Ulcerative Colitis. Response to treatment will be evaluated using the change from baseline in Total Mayo score at week 8 based on the mITT population. The baseline value is defined as the last value obtained on or before the date and time of the first study drug dose. Descriptive statistics will be presented including mean, standard deviation (SD), median, max, and min by treatment and cohort group (and overall cohort) at each timepoint. However, to allow for a direct comparison of BBT-401-1S vs placebo for each cohort, descriptive statistics will be provided for the difference in the change from baseline between the treatment groups during the double-blind portion of the study.

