### 9.5.2 Analysis of Secondary Endpoints

The secondary efficacy analyses will be based on the mITT population. Analysis on the TEAEs and other safety endpoints is discussed under the Safety Analysis section below.

For each efficacy endpoint, descriptive statistics will be presented by treatment and cohort group (and overall cohort) at each timepoint, including mean, SD, median, max, and min as there is no formal inferential statistical analysis is planned.

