5 CHANGES TO PROTOCOL-SPECIFIED ANALYSES

No changes to protocol-specified analyses are planned.

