6 LIST OF TABLES AND FIGURES

List of Tables

ICH Heading	Table Number	Table Description
14.1	14.1.1	DEMOGRAPHIC Summary of Patient Disposition (All Patients)
	14.1.2	Summary of Demographic and Baseline Characteristics (mITT Analysis set)
	14.1.3	Summary of Medical History (mITT Analysis set)
	14.1.4	Summary of Prior Medications (mITT Analysis set)
	14.1.5	Summary of Concomitant Medications (mITT Analysis set)
14.2		EFFICACY
14.2.1	14.2.1.1	Primary Efficacy Summary of Change of Total Mayo Score from Baseline to Week 8 (mITT Analysis set)
	14.2.1.2	Summary of Change of Total Mayo Score from Baseline to Week 8 (PP Analysis set)
14.2.2		Secondary Efficacy
	14.2.2.1.1	Summary of Change of Partial Mayo Score from Baseline to Week 8 (mITT Analysis set)
	14.2.2.1.2	Summary of Change of Partial Mayo Score from Baseline to Week 8 (PP Analysis set)

- 14.2.2.2.1 Summary of Change of Histologic Assessment of Endoscopic Biopsy from Baseline to Week 8 (mITT Analysis set)
- 14.2.2.2.2 Summary of Change of Histologic Assessment of Endoscopic Biopsy from Baseline to Week 8 (PP Analysis set)
- 14.2.2.3.1 Summary of Change of Ulcerative Colitis Endoscopic Index of Severity (UCEIS) Score from Baseline to Week 8 (mITT Analysis set)
- 14.2.2.3.2 Summary of Change of Ulcerative Colitis Endoscopic Index of Severity (UCEIS) Score from Baseline to Week 8 (PP Analysis set)
- 14.2.2.4.1 Summary of Change of Short Inflammatory Bowel Disease Questionnaire (SIBDQ) from Baseline to Week 8 (mITT Analysis set)
- 14.2.2.4.2 Summary of Change of Short Inflammatory Bowel Disease Questionnaire (SIBDQ) from Baseline to Week 8 (PP Analysis set)
- 14.2.3 Exploratory Efficacy**
 - 14.2.3.1 Summary of Change of Concentration of Biomarkers from Baseline to Week 8 (mITT Analysis set)
 - 14.2.3.2 Summary of Change of Concentration of Biomarkers from Baseline to Week 8 (PP Analysis set)
- 14.3 SAFETY**
 - 14.3.1 Display of Adverse Events**
 - 14.3.1.1 Overall Summary of Treatment-Emergent Adverse Events up to Week 8 (Safety Analysis set)
 - 14.3.1.2 Summary of Treatment-Emergent Adverse Events up to Week 8 by System Organ Class and Preferred Term (Safety Analysis set)
 - 14.3.1.3 Summary of Treatment-Emergent Adverse Events up to Week 8 by System Organ Class, Preferred Term, and Severity (Safety Analysis set)
 - 14.3.1.4 Summary of Treatment-Emergent Adverse Events up to Week 8 by System Organ Class, Preferred Term, and Relationship to Study Drug (Safety Analysis set)

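### The SAP tabulates efficacy and TEAEs only to Week 8, although the protocol promises by-visit efficacy summaries, and it declares no change

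*SAP*

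**What the plan says.** **Schedule.** Protocol 8.3 has two kinds of efficacy measure. Total Mayo, histology and UCEIS are taken at Screening and Week 8. The others are repeated through treatment: "Partial Mayo Score: Baseline, W4, W8, W12, and W16"; "SIBDQ: Baseline, W4, W8, W12, and W16"; "Serum CRP: Baseline, W4, W8, W12, and W16". Fecal calprotectin and fecal lactoferrin follow the same schedule.

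**Treatment sequence.** Protocol 4.1 keeps the active group on drug to Week 12 and then gives placebo for 4 weeks. The placebo group moves to drug after Week 8.

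**Protocol analysis text.** Section 9.5.2 says: "For each efficacy endpoint, descriptive statistics will be presented by treatment and cohort group (and overall cohort) at each timepoint". Section 9.5.1 uses the same by-visit phrase, but only for Total Mayo. Section 9.5.7 says biomarkers get no formal analysis and will be listed.

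**SAP.** Section 4.7.2 defines each secondary efficacy endpoint as the change to Week 8 and drops the by-visit commitment. Every efficacy and biomarker table in Section 6 has a Week 8 title, for example "Summary of Change of Partial Mayo Score from Baseline to Week 8 (mITT Analysis set". The shells contain only Baseline, Week 8 and the change between them. Section 4.9 says biomarker data will be listed. Section 5 reads: "No changes to protocol-specified analyses are planned".

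**TEAEs.** The six tables 14.3.1.1 to 14.3.1.6 all end at Week 8. Protocol 9.5 and SAP 2.2.2 name the endpoint as TEAEs to Week 8. Protocol 9.5.3 and SAP 4.8.1 define TEAEs with no end date. The Protocol Section 3 table extends the period to eight weeks after the last dose.

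**The concern.** The SAP leaves out summaries that the protocol promises and then says nothing has changed. A reader of the final tables would not know that the protocol called for more.

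Week 4 is the only other post-baseline visit inside the randomised, placebo-controlled period, so it bears on onset of effect. Weeks 12 and 16 cover longer treatment, the placebo group's move to drug, and the active group's move to placebo. The design built in those switches, and patients attend visits and give samples for them. Without prespecified tables, any account of this period will be assembled after unblinding, with free choice of measure and visit.

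For adverse events, safety is part of the primary objective. All of the placebo group's time on drug, and the active group's last 4 weeks on drug, fall outside every TEAE table.

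**Working it through.** The plan states no figure for this point and has no power calculation, so there is nothing to reproduce. The check is a comparison of texts followed by two counts.

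**1. Texts side by side**

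| Measure | Post-baseline visits (Protocol 8.3) | Protocol summary | SAP table |
|---|---|---|---|
| Total Mayo | W8 | each timepoint (9.5.1) | W8: complete |
| Histology, UCEIS | W8 | each timepoint (9.5.2) | W8: complete |
| Partial Mayo, SIBDQ | W4, W8, W12, W16 | each timepoint (9.5.2) | W8 only |
| CRP, fecal calprotectin, fecal lactoferrin | W4, W8, W12, W16 | 9.5.2 if treated as efficacy; listing in 9.5.7 | W8 only |

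**2. Endpoint-by-visit count**

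- Scheduled: 5 measures × 4 visits + 3 measures × 1 visit = 20 + 3 = 23.
- Tabulated: 8, all at Week 8.
- Not tabulated: 23 − 8 = 15.
  - Clear departure (Partial Mayo, SIBDQ): 2 × 3 = 6.
  - Probable departure (three biomarkers): 3 × 3 = 9.
- Of the 15, those after the placebo group's switch (W12, W16): 5 × 2 = 10.
- Of the 15, those after the active group's switch (W16): 5 × 1 = 5.
- Efficacy summaries planned after either switch: 0.

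**3. Could other SAP text supply the missing summaries?**

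- The model in SAP 4.7.1 is called MMRM but lists no visit term, and its shells report Week 8 only.
- The shells were made for the 1st cohort, but SAP 4.7.2 and the Section 6 list carry the same Week 8 limit.
- SAP 4.1 allows ad hoc analyses, which is not prespecification.
- Listings 16.2.6.2, 16.2.6.5 and 16.2.6.6 have a visit column, so individual values are shown. They do not give the mean, SD, median and range.

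**4. TEAE coverage**

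Inputs: 3 cohorts of 12 active and 4 placebo (Protocol 6.3), so 36 active and 12 placebo. Assume full enrolment and no dropout.

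- Patient-weeks on drug: 36 × 12 + 12 × 8 = 432 + 96 = 528.
- Of these, after Week 8: 36 × 4 + 12 × 8 = 144 + 96 = 240.
- Share: 240 / 528 = 45%.
- Per cohort: (12 × 4 + 4 × 8) / (12 × 12 + 4 × 8) = 80 / 176 = 45%, so the share does not depend on how many cohorts run.

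**5. TEAE period**

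The documents give three periods: to Week 8; no end date; and eight weeks after the last dose. Protocol 8.5.4 collects events until the end-of-study visit, and the safety follow-up visit is 2 weeks (+7 days) after the last dose. The third period therefore runs beyond scheduled collection.

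**The case against.** **Named endpoints are all at Week 8.** True, and the SAP matches them. Protocol 9.5.1 also directs the between-group comparison to the double-blind portion. The departure is from the separate by-visit commitment in 9.5.2, not from an endpoint definition.

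**Biomarkers.** If Protocol 9.5.7 governs, a Week 8 table plus listings already exceeds what was promised, and only 6 summaries are missing. This is a fair reading. Against it, Protocol 8.3 lists these markers as efficacy assessments, Protocol 9.1 includes biomarker measures in the descriptive statistics, and the SAP tabulates them under an efficacy heading. They are probably covered, but not certainly.

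**TEAEs.** The tables agree with the endpoint named in Protocol 9.5, so this is not a plain breach. What stands is that Protocol 9.5.3 and SAP 4.8.1 set no Week 8 limit, and Protocol Section 3 gives a longer period.

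**Limited value after Week 8.** There is no concurrent placebo-controlled comparison after Week 8. Steroid tapering is possible from then on, and codes may already be open to the sponsor. Loss of effect off drug rests on one visit. With 4 placebo patients per cohort, a listing already shows much of what a mean would. All this argues for keeping the tables descriptive. It does not apply to Week 4.

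**Stronger readings to resist.** A reader might infer that the second half of treatment is never summarised. The documents do not support that: laboratory, vital sign, ECG and physical examination tables are by visit, disposition reports Week 16 completion, and efficacy values are listed. A reader might also infer from Protocol 9.5.1 that the primary endpoint is affected. It is not, because Total Mayo has no post-baseline visit other than Week 8.

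**Conclusion.** The point holds within limits. The SAP omits, without declaring it, 6 promised summaries (Partial Mayo and SIBDQ at Weeks 4, 12 and 16) and probably 9 more for CRP and the fecal markers. No efficacy summary is planned after either treatment switch. No primary result, named endpoint or dose decision changes.

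For TEAEs, the fault is an unresolved conflict over the reporting period. Its effect is that about 45% of planned patient-weeks on drug have no TEAE table. That share assumes full enrolment and no dropout. Early withdrawals would change it, and the documents give no dropout rate.

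This should be corrected, because the tables are promised or clearly useful and the data will be in hand.

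**What to change.** 1. In the Partial Mayo and SIBDQ tables, add rows for Weeks 4, 12 and 16 with value and change from baseline, descriptive only. Do the same in the biomarker tables, and state in SAP 4.9 that biomarkers are summarised as well as listed.
2. Present these by randomised group, with Weeks 12 and 16 labelled by the treatment being taken.
3. Add descriptive TEAE tables from Week 8 to safety follow-up, by treatment at onset, and keep the Week 8 tables for the named endpoint.
4. Reconcile the TEAE period across Protocol Section 3, Protocol 9.5 and 9.5.3, SAP 2.2.2 and SAP 4.8.1.
5. Correct SAP Section 5. If the sponsor prefers to keep any Week 8 restriction, declare and justify it there. Changes made after unblinding go in the study report with reasons, as Protocol Section 9 already requires.

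**Cost.** A few more rows and tables; no new patients, visits or samples. The by-visit layout already exists in the safety shells. The downside is that small, uncontrolled post-Week-8 summaries could be over-read, so they should carry no p-values or between-group tests.
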